3.2. SECONDARY OUTCOMES MEASURES

Secondary endpoints will be:

- The incremental cost/Qaly of PUL compared to transurethral surgery at 12 months
- The total hospital cost of each surgery procedure based on a top down micro-costing method performed during hospitalization stay
- Overall and specific urogenital healthcare consumptions at 4 months, 1 year and 3 years following the surgical procedure
 - Dispensed medications identified using the corresponding codes of the Anatomical Therapeutic Chemical (ATC) Classification;
 - o In- and out-patient visits;
 - Hospitalisation and their corresponding discharge diagnoses coded according to International Classification of Disease, 10th revision;
 - Medical procedures;
 - Nursing acts and physiotherapy;
 - Medical imageries and lab tests;
 - Transport;
 - Sick allowances;
 - At 4 months: all healthcare consumptions which are not reimbursed, but payed by the patient (e.g.: urinary incontinence products).

• BPH retreatment,

• Any dispensing of the following medications at 1 and 3 years after surgical procedure: alpha-blockers (ATC code G04CA) or 5-alpha-reductase inhibitors (ATC code G04CB);

 Hospitalization at 1 and 3 years after surgical procedure, with the main diagnosis of BPH (ICD-10 code N40) and the surgical procedure codes JGNE003, JGNE171, JGNJ001, JGFA005 JGFA009, JGFA015, JGFE023, JGFE365.

Urinary symptoms,

- Urinary incontinence evolution between inclusion and 4 months after surgical procedure (Incontinence Severity Index (ISI));
- International consultation on Incontinence questionnaire for Urinary incontinence short form (ICIQ-UI SF)
- Hospitalization with a discharge diagnosis ICD-10 code related to an urinary infection (code N41 for acute prostatitis or code N10 for acute pyelonephritis) at 1 and 3 years after surgical procedure;
- Hospitalization with a discharge diagnosis ICD-10 code related to urinary retention (R33) at 1 and 3 years after surgical procedure;
- Hospitalization with a discharge diagnosis ICD-10 code and/or medical procedure related to urethral stricture at 1 and 3 years after surgical procedure.

• Global quality of life,

- IPSS and IPSS-Q8 evolution between inclusion, 4 month, and 1 year after surgical procedure;
- O Jenkins sleep questionnaire between inclusion, 4 months, and 1 year after surgical procedure;
- EQ-5D-5L questionnaire (appendix 2) evolution between inclusion, 4 months, and 1 year after surgical procedure;

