4.2. METHODOLOGY OF ECONOMIC EVALUATION

The economic evaluation will be conducted from the French Healthcare System point of view. This means that all healthcare expenditures and costs assumed by the French Healthcare Insurance, hospitals and patients will be taken into account in the analysis.

The incremental cost/avoided complication at 4 months between the PUL and TURP/laser cohorts, will be based on the following criteria:

• Differences in costs between both strategies:

- A micro-costing measurement will be performed in both groups during hospital stay to provide the total cost of each procedure. To identify costs, we will directly observe the resources used during the hospital stay that are related to each surgical procedure including human resources, materials, consumables and equipment.... Because it will not be possible to perform micro-costing for all items over the whole hospital stay, we will also use gross-cost hospital databases for some items (laundry, bedrooms, catering, general daily care, hospital equipment). Although it would be relevant to carry out a multicentric analysis on all recruiting centers, we prefer to restrict this analysis to the patients participating in the study in 3 hospitals: Bordeaux, Lyon and Lille University Hospitals and one clinic, the clinic la Croix du Sud at Quint Fonsegrives. This is justified because this kind of surgery seems to be standardized and doesn't vary a lot from one surgeon to another. Furthermore it will be easier to organise data collection in these centers, which are very used to economic studies. We intend to collect data for 5 patients/surgeries in each group, which means a total of 30 patients/surgeries included in the costing study. This choice could induce a lack of representativeness that we will study carefully by 2 ways before drawing our conclusions in the final report: 1- during collection data: we will study the variability of surgical practices through the filling of micro-costing questionnaires. If, at the end of the 30 observations, the questionnaires are very heterogeneous, we will continue to collect data in order to ensure representativeness of our costing study 2during statistical analysis, we will perform sensitivity analyses on cost data.

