- Ouring the first 4 months after hospital discharge all expenses related to healthcare consumptions, reimbursed and not reimbursed, will be systematically collected at each follow-up visits by the participant of the study. Follow-up visits will be scheduled every month (including phone call with clinical research assistant and medical appointments).

• Differences in complications:

Complications will be classified according to the Clavien Dindo classification of adverse events.

The incremental cost/Qaly at 1 year between the PUL and TURP/laser cohorts will be based on the following criteria:

Differences in costs between both strategies:

- The total cost of hospitalization assessed by the micro-costing method described before.
- During the 12 months after hospital discharge all reimbursed expenses related to healthcare consumptions of each participant in each cohort will be gathered using SNDS claims databases.

• Differences in Qaly:

• The EQ-5D-5L questionnaire (appendix 2) will be fulfilled by the participants at the inclusion, at 4 months and at 1 year after initial surgery.

Statistical methods associated with this economic evaluation are described in chapter 11.

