9.2. SUMMARY TABLE OF ASSESSEMENTS

Assessments carried out as part of the care (C) or specifically for research (R).

rissessments carried out as			V1	V2	V3	V4	V5
	Inclusion	Intervention	Month 1	Month 2	Month 3	Month 4	Month 12
			(+/- 7 days)	(+/- 7 days)	(+/- 7 days)	(+/- 7 days)	(+/- 14 days)
Patient information (R)	✓						
Informed consent (R)	✓						
Verification of eligibility criteria (R)	1						
Medical and surgical history (R)	1						
Drugs whether or not related to BPH (R)	1	✓	1	1	1	1	✓
Recovery after surgery (R)			✓	✓	✓	✓	
Clinical examination (C)	✓					✓	✓
Biological examination ¹ (C)	✓					✓	1
Urinary flowmetry (C)	✓					✓	✓
Urinary tract ultrasound (C)	✓						
Urine microscopic examination (C)	1	√					
Functional and quality of life questionnaires ² (R)	1					1	√
Complications and adverse effects (R)		/	1	1	1	1	✓
Cost of hospitalization (R)		√					
Health care consumptions (declared by the patient) (R)			1	1	1	1	

¹Blood sample tests: total PSA and creatinine dosage

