9.4. INTERVENTION

The surgical procedure will be performed during hospitalisation in an operating theatre. The micro-costing data will be collected during the time of intervention, on the basis of a micro-costing questionnaire developed by the project team. By the end of hospitalisation for the surgical procedure, participant will be provided with a participant diary/book to self-report of healthcare consumptions (medications, hospitalizations, out-patient visits, radiology and biology exams, not reimbursed treatments ...) and QoR-VAS until Visit 4.

9.5. VISITS 1, 2 AND 3

Visit 1, 2 and 3 will be phone call visits performed by the Clinical Research Assistant.

It will be collected according to participant notification:

- All medication in relation with BPH or with the intervention
- All healthcare consumption between two visits
- The QoR-VAS completed by the participant at home
- Any complication or adverse effect will need to be confirmed by a medical doctor and classified according to the Clavien Dindo classification

9.6. VISIT 4

Visit 4 will be performed at the outpatient clinic by a certified urologist at month 4 (+/- 7 days).

- Participants will undergo urinary flowmetry
- Participants will undergo standard physical examination including digital rectal examination, abdominal palpation and lumbar percussion.
- Participants will complete the following standard questionnaires (part of care):
 - o IPSS score
 - o IPSS Q8
 - o ISI (Incontinence symptom index)
 - o ICIQ-UI SF
 - o MSHQ-Ejd
 - o IIEF15
 - o QoR-VAS
 - o EO-5D-5L
 - o Jenkins sleep scale
- Investigator will collect:
 - o Any adverse effect and complications based on Clavien Dindo classification
 - o All medication in relation with BPH or with the intervention
 - o All healthcare consumptions since visit 3

9.7. VISIT 5

Visit 5 will be performed at the outpatient clinic by a certified urologist at month 12 (+/- 14 days).

- Participants will undergo urinary flowmetry
- Participants will undergo standard physical examination including digital rectal examination, abdominal palpation and lumbar percussion.
- Participants will complete the following standard questionnaires (part of care):
 - o IPSS score
 - o IPSS Q8

- o ISI (Incontinence symptom index)
- o ICIO-UI SF
- o MSHQ-Eid
- o IIEF15
- o QoR-VAS
- o EQ-5D-5L
- o Jenkins sleep scale
- Investigator will collect:
 - o Any adverse effect and complications based on Clavien Dindo classification

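### Protocol section 4.2 includes patients' costs in its perspective, but the post-discharge cost in the secondary 12-month cost/QALY ratio is limited to reimbursed SNDS expenses

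*Protocol*

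**What the plan says.** Protocol section 4.2 fixes a single perspective at the start of the economic methods: "all healthcare expenditures and costs assumed by the French Healthcare Insurance, hospitals and patients will be taken into account in the analysis". It makes no exception by time horizon or by ratio.

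The same section then lists the cost components of each ratio.

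- **4-month ratio (primary, cost per avoided complication).** The hospital stay is micro-costed. For the first four months after discharge, "all expenses related to healthcare consumptions, reimbursed and not reimbursed, will be systematically collected at each follow-up visits by the participant of the study".
- **12-month ratio (secondary, cost/QALY).** The stay is again micro-costed: "The total cost of hospitalization assessed by the micro-costing method described before". For the 12 months after discharge, "all reimbursed expenses related to healthcare consumptions of each participant in each cohort will be gathered using SNDS claims databases". No third component is listed.

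The data collection agrees with the narrower 12-month definition. Section 3.2 gives the unreimbursed item one time point: "At 4 months: all healthcare consumptions which are not reimbursed, but payed by the patient (e.g.: urinary incontinence products". Under section 9.4, the participant diary records "not reimbursed treatments ...) and QoR-VAS until Visit 4". In the section 9.2 table, patient-declared consumption is ticked four times, matching visits 1 to 4. The visit 5 list in section 9.7 asks about complications and related medication, but has no item on healthcare consumption.

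**The concern.** The protocol itself fixes both the perspective and the cost components, and they do not agree. This is not detail left to the analysis plan: an analysis plan that followed the 12-month component list would depart from the stated perspective.

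Two things are at stake. First, a reader of the cost/QALY result would take it to include what patients pay, and it would not. Section 1.3 presents this ratio as one that public decision makers need, and section 1.1.2.3 says the economic data are meant for the reimbursement file. Second, the omitted cost need not cancel between cohorts. The protocol's own example of an unreimbursed item is incontinence products. Section 1.5 expects incontinence to be no worse, and probably less frequent, after PUL, and section 1.1.2.1 counts incontinence among the delayed complications seen after the first three months.

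**Working it through.** The documents state no figure that could be reproduced. The check sets the text side by side, followed by simple algebra.

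**Components against the stated perspective**

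| Cost component | Perspective (4.2) | 4-month ratio (4.2) | 12-month ratio (4.2) |
|---|---|---|---|
| Index hospital stay | included | micro-costed | micro-costed |
| Reimbursed, after discharge | included | included, participant report | included, SNDS claims |
| Unreimbursed, months 0–4 | included | included | not listed, though collected |
| Unreimbursed, months 5–12 | included | outside the horizon | not listed and not collected |

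**Could another section supply the missing rows?** Section 6 describes SNDS outpatient content as reimbursed expenditure, so claims cannot supply items that were never reimbursed. Section 11.2.3 says the 12-month ratio is assessed in the same way as the 4-month one. That sentence follows the formula ΔC/ΔE and carries over the formula; it adds no cost component. Neither section closes the gap.

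**What the omission does to the totals.** Let H be the stay, R reimbursed and U unreimbursed cost after discharge.

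- 4-month cost: H + R(0–4) + U(0–4)
- 12-month cost as written: H + R(0–12)
- Difference (12-month minus 4-month): R(5–12) − U(0–4), if participant report and claims agree on R(0–4)

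A man's 12-month cost falls below his 4-month cost only if his unreimbursed spending to month 4 exceeds all his reimbursed spending in months 5–12.

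**What it does to the ratio.** Let d be the between-cohort difference in mean unreimbursed cost over 12 months. The omission moves the cost/QALY ratio by d/ΔQALY in absolute size, and the incremental net monetary benefit by d at every threshold λ.

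**Illustration on assumed values only.** None of these inputs is in the documents, apart from the implant cost in section 1.1.2.3.

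- Assumed spending in affected men is 20–60 euro a month, and the assumed difference in the share affected is 5–15 points.
- Low: 0.05 × (20 × 12) = 12 euro. High: 0.15 × (60 × 12) = 108 euro.
- Implants: 4 × 500 = 2,000 euro. So d is 12/2,000 = 0.6% to 108/2,000 = 5.4% of that.
- With an assumed ΔQALY of 0.05, the ratio shifts by 12/0.05 = 240 to 108/0.05 = 2,160 euro per QALY.
- With an assumed ΔQALY of 0.01, it shifts by 12/0.01 = 1,200 to 108/0.01 = 10,800 euro per QALY.
- If the share affected is the same in both cohorts, d from this source is 0 and so is the shift.

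Section 11.2.3 plots acceptability from 0 to 30,000 euro. On these assumptions the effect runs from nothing to something visible. The larger shifts come from the small assumed denominator.

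**The case against.** The strongest reply is that the data plan is coherent and only the general perspective sentence is too broad. Sections 3.2, 9.2 and 9.4 all stop unreimbursed collection at month 4, and section 1.3 explains why claims are used for longer follow-up. The two ratios also differ in denominator, horizon and status, and the protocol never pools them, so different cost scopes are not in themselves an error. It can be added that section 4.2 says what will be drawn from SNDS without expressly excluding the diary costs already held.

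Most of this is fair, and it limits the point. It does not remove it: the perspective carries no time limit, the 12-month list is explicit, and nothing says the diary costs are added.

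A reader might infer three stronger things that the documents do not support.

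- **That the whole 12-month cost is reimbursed claims.** It is not. The micro-costed stay is included, and the limit applies to post-discharge cost.
- **That the cost/QALY result is materially biased, or that 12-month totals will commonly fall below 4-month totals.** No patient-paid amount or QALY difference is given, a zero difference is compatible with section 1.5, and the reversal needs the condition shown in the working.
- **That a new question at visit 5 would solve it.** Version 6.0 is dated 31/01/2023, and the summary calendar starts inclusion in Q2 2021. On that calendar the earliest participants had already passed month 12. The others would have to recall eight months of spending.

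**Conclusion.** The contradiction stands. The perspective in section 4.2 includes patients' costs, while the post-discharge cost in the 12-month cost/QALY ratio is limited to reimbursed SNDS expenses, added to the micro-costed stay. As written, that ratio does not have the stated perspective and leaves out unreimbursed costs already collected to month 4.

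It concerns a secondary outcome; the primary 4-month ratio is unaffected. The size cannot be derived from the documents and may be negligible. The illustrative euro ranges rest wholly on assumptions and are not evidence of importance. The case for changing the text is that the rule and the perspective disagree, and that the correction costs little.

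**What to change.** Reconcile the two statements in section 4.2 in one of two ways.

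1. **Preferred.** Define the 12-month cost as the micro-costed stay + SNDS reimbursed costs to month 12 + patient-declared unreimbursed costs to month 4. Add a sensitivity analysis that carries each participant's month-4 monthly unreimbursed amount forward over months 5–12 (eight times that amount). State that patient-paid costs after month 4 are not observed.
2. **Otherwise.** Restate the 12-month perspective as limited to the micro-costed hospital stay and reimbursed expenses, and report the 4-month cost on that same basis as a sensitivity analysis. Naming the components is safer than calling this an insurer-and-hospital perspective, because the documents do not settle whether reimbursed expenses include any patient share.

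Either way the cost is protocol or analysis plan wording and a few lines of analysis, with no new data collection. The downside of the first option is that months 5–12 rest on an assumption: carrying the month-4 amount forward overstates the cost if spending falls as men recover, and understates it if late complications add to it. The main 12-month total under that option would still omit patient-paid costs after month 4, which is why the text must say so.

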5. ELIGIBILITY CRITERIA

5.1. PUL AND TURP/LASER COHORTS

5.1.1. INCLUSION CRITERIA

- Male Gender
- Diagnosis of symptomatic BPH requiring a surgical procedure by PUL or TURP/laser
- Age > 50 years
- International Prostatic Symptom Score ≥14
- Peak urine flow rate ≤ 15 ml/sec on a bladder repletion volume ≥ 150 ml

Prostate volume >30cc to <80 cc per ultrasound or RMI (within 6 months before patient inclusion).

• Affiliated to a French health insurance system

5.1.2. EXCLUSION CRITERIA

- Current urinary retention
- Post void residual urine > 250ml
- Active urinary tract infection at time of treatment

- Previous BPH procedure
- Urethral conditions that may prevent insertion and delivery of device system into bladder (i.e. urethral strictures, meatal stenosis, bladder neck contracture)
- Previous pelvic surgery or irradiation
- History of neurogenic or atonic bladder
- Biopsy of the prostate within the past 6 weeks
- Life expectancy estimated to be less than 1 year
- History of prostate or bladder cancer
- PSA>10ng/ml unless prostate biopsy is negative
- Person intending to move abroad within 1 year after inclusion
- Person placed under guardianship or curatorship
- Person participating to another interventional study on benign prostatic hyperplasia during the study

Patients of the PUL and TURP/LASER cohorts will be identified in the SNDS through their NIR national identifier (if possible) or using a probabilistic linkage with age, hospital identifier (FINESS), date of hospitalization for the procedure and ICD-10 discharge diagnosis. Only patients with a 2-year history before the procedure and a 3-year follow-up after the procedure will be analyzed.

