	Exclusion criteria: Patients with current urinary retention, post void residual urine > 250ml, active urinary tract infection at time of treatment, previous BPH procedure, urethral conditions that may prevent insertion and delivery of device system into bladder, previous		

Version no.6.0 of 31/01/2023 pelvic surgery or irradiation, history of neurogenic or atonic bladder, biopsy of the prostate within the past 6 weeks, life expectancy estimated to be less than 1 year, history of prostate or bladder cancer, PSA>10ng/ml unless prostate biopsy is negative, person guardianship or curatorship will not be included in the cohorts. Patients intending to move abroad within 1 year after inclusion will not be included either. Person participating to another interventional study on benign prostatic hyperplasia during the study. Patients of the PUL and TURP/LASER cohorts will be identified in the SNDS through their NIR national identifier (if possible) or using a probabilistic linkage with age, hospital identifier (FINESS), date of hospitalization for the procedure and ICD-10 discharge diagnosis. Only patients with a 2-year history before the procedure and a 3-year follow-up after the procedure will be analysed. The SNDS cohort: Inclusion criteria: male patients affiliated to a French health

insurance system aged over 50 years who experienced a TURP/Laser surgery in first line of treatment for a symptomatic BPH in the same period as patients of the PUL and TURP/LASER cohorts.

Exclusion criteria: Patients hospitalized in one of the 7 investigational centers and patients with a previous BPH procedure, a previous pelvic surgery or irradiation, history of prostate or bladder cancer within the 2 previous years, a biopsy of the prostate within the past 6 weeks, or with a short life expectancy will not be included in the

Matching criteria: A total of 5 patients will be matched to 1 patient of the PUL cohort for each procedure (TURP, HLE, GLV) according to age, date of the procedure (same month) and a high dimensional disease risk score (hDRS) based on the one-year SNDS information before the transurethral procedure.

RESEARCH PROCEDURES/ **STRATEGIES**

OUTCOMES

The studied procedures are:

- The experimental procedure: PUL, consisting in transurethral placement of permanent UroLift implants into the lobes of the prostate. The intent of PUL procedure is to retract the lobes of the prostate in order to reduce prostatic obstruction.

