STUDY SIZE	• 1200 patients in the SNDS cohort: 400 transurethral resection, 400 laser enucleation, 400 laser vaporization		
Investigational centers	 7investigational centers CHU de Bordeaux – [name] CHU de Lyon – [name] CHU de Montpellier – [name] CHU de Lille – [name] Hôpital Cochin, APHP – [name] CHU de Tours – [name] Clinique La croix du Sud – [name] 		
DURATION OF THE RESEARCH PROJECT	 For the PUL and TURP/Laser cohorts (prospective interventional study) Recruitment: 32 months Clinical follow-up: 12 months 		

0	SNDS	database	follow-up:	3	years
---	-------------	----------	------------	---	-------

SNDS database history: 2 years

For the SNDS cohort

o Inclusion date: date of the surgical procedure completion

o Follow-up: 3 years

o History: 2 years

- Regulatory aspects Q4 2019 Q2 2020
- Inclusion period of PUL and TURP cohorts Q2 2021-Q2 2023
- Clinical data analysis
 - Primary endpoint data (4 months after surgical procedure) Q4 2023
 - Data management and statistical analysis for primary endpoint O1-O2 2024
 - Data management and statistical analysis for clinical data Q3-Q4 2024
- SNDS data extraction and analysis
 - o Statistical Analysis Plan Q1 2023
 - o 1st Data extraction (1-year follow-up) Q4 2025
 - O Data management and interim statistical analysis Q1-Q2 2026
 - Interim study report Q3 2026
 - o 2nd Data extraction (3-year follow-up) Q4 2027
 - Data management and final statistical analysis Q1-Q2 2028
- Final study report Q3 2028

The analyses will be performed for each cohort, according to the matched treatment group and will include:

- A description of study populations
- A comparison of baseline characteristics between the PUL and the TURP cohorts
- A comparison of baseline characteristics between the PUL and the SDNS cohorts before and after hDRS matching (flow-chart, baseline characteristics);
- An Estimation of cost effectiveness ratios between the PUL and TURP/laser cohorts at 4 months and 1 year.
- An estimation of the cost of hospitalization related to each surgery procedure during hospital stay
- A description of the overall and specific urogenital healthcare

DATA ANALYSIS

	consumptions;		
	o a description of BPH retreatments;		
	o a description of urinary symptoms;		
	o a description of the quality of life;		
	 a description of the time to recovery after surgery and to return to normal professional activities; 		
	o a description of the sexual side effects;		

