5.2.2. EXCLUSION CRITERIA

- Patients hospitalized in one of the 7 investigational centers
- Patients with a previous BPH procedure previous pelvic surgery or irradiation, history of prostate or bladder cancer (2-year database history and/or Long term disease registration)
- Patients with biopsy of the prostate within the past 6 weeks
- Patients with short life expectancy based on a Charlson Comorbidity Index ≥ 10 (this threshold reflects the presence of metastasis or an equivalent health condition) (cf. Bannay and al., 2015).

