9.8. SNDS ASSESSMENTS

For each patient identified in the SNDS cohort, the following settings will be defined:

- Inclusion date: date of the surgical procedure completion
- **Look-back period:** 2 years preceding the inclusion date;
- **Follow-up period:** 3 years following the inclusion date.

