9.10.4. OTHER DEVIATIONS

Protocol deviations should be documented and justified.

Violations are considered major deviations in:

- regulatory aspects,
- the primary endpoint.

All major violations are subject to a presentation to the steering committee to decide whether the patient's data can be exploited.

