11.2. STATISTICAL METHODS EMPLOYED

11.2.1. GENERALITIES

Statistical analysis will be performed using SAS® software (SAS Institute, latest current version, North Carolina, USA). Qualitative and ordinal variables will be summarized by frequencies and proportions of each modality, taking into account missingness as a modality. Continuous variables will be summarized by size, number of patients with missing data, arithmetic mean, standard deviation, median, interquartile ranges and extreme values. Confidence intervals will be estimated using Normal approximation for quantitative and qualitative relevant parameters, or bootstrapping method for costs when count < 100 patients.

Standardized mean differences (*Rosenbaum*, *Rubin*, 1985) will be estimated to measure the effect size of quantitative and qualitative baseline characteristics between groups (PUL and TURP cohorts, matched patients of PUL and SNDS cohorts).

For confidence intervals, 2-sided confidence level of 95% will be used. For all tests, a 2-sided significance level of 5% will be used:

- Proportions will be compared between two independent groups using Pearson's Chi-2 test (or Fisher's exact test when expected counts are < 5)
- Means will be compared between two independent groups using Student's t-test when normal distribution is followed (or Mann-Whitney's test when normal distribution is not followed)
- Occurrence of events (retreatment, urinary symptoms) will be estimated across time using Kaplan-Meier estimator and compared between groups with logrank test.
- Adjusted comparisons between PUL and the TURP/Laser cohorts and between PUL and SNDS cohorts will be
 performed in intention-to-treat analysis using linear regression model when it involves quantitative variables,
 and using logistic regression model adjusted on potential confounders when it involves qualitative variables.

[figure not shown]
A Statistical Analysis Plan (SAP) will be developed and will be validated before the analyses.

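### The protocol restricts the SNDS-linked analysis of the PUL and TURP/laser cohorts to patients with 3 years of follow-up, a selection on post-surgery events that is not stated for the SNDS comparators

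*Protocol*

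**What the plan says.** Section 5.1.2, at the end of the criteria for the PUL and TURP/laser cohorts and directly after the sentence on linkage to the SNDS, states: "Only patients with a 2-year history before the procedure and a 3-year follow-up after the procedure will be analyzed". The Summary, under study population, has the same sentence: "Only patients with a 2-year history before the procedure and a 3-year follow-up after the procedure will be analysed".

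For the SNDS cohort, Sections 5.2.1 to 5.2.3 contain no condition on follow-up. Section 9.8 sets the follow-up period as "3 years following the inclusion date", which is a window and not a requirement for being analysed. The nearest exclusion is a baseline one: "Patients with short life expectancy based on a Charlson Comorbidity Index ≥ 10". The corresponding baseline exclusion for the two clinical cohorts is "Life expectancy estimated to be less than 1 year".

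Section 11.2.1 calls the adjusted PUL versus TURP/laser and PUL versus SNDS comparisons intention-to-treat. It also plans: "Occurrence of events (retreatment, urinary symptoms) will be estimated across time using Kaplan-Meier estimator", with a logrank test between groups. The Summary's timetable has two SNDS extractions, the first being "1st Data extraction (1-year follow-up) Q4 2025" and the second, for 3-year follow-up, in Q4 2027.

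**The concern.** Whether a patient has 3 years of follow-up is known only after surgery. Making it a condition of analysis selects patients on what happened to them after treatment. The baseline exclusions do not make this harmless: men expected to live more than 1 year can still die within 3.

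The condition is written for the clinical cohorts only. On the wording, the 3-year PUL versus SNDS comparison would set PUL patients who survived and stayed in the database against comparators with no stated survival condition. Excess cost or events among men who die would then count on one side only. Between PUL and TURP/laser the rule is symmetric, but it can still bias that comparison if deaths differ by procedure.

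The outcomes exposed are the 3-year secondary ones: healthcare consumption, BPH retreatment, and hospitalisation for infection, retention or stricture. Read literally, the rule also reaches the 12-month cost/QALY analysis, because Section 4.2 takes its post-discharge costs from the SNDS. The results are intended to support reimbursement, so a one-sided selection matters even for secondary outcomes.

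**Working it through.** **1. The plan's own precision figures.** The half-width is 1.96·√(p(1−p)/n). With n = 80 it is 6.57% at p = 10% and 10.96% at p = 50%; Section 11.1 states 7% and 11%. With n = 400 it is 2.94% and 4.90%; stated 3% and 5%. Matching gives 80 × 5 = 400 per procedure and 400 × 3 = 1200. The sample-size section reproduces, so the issue is who is analysed.

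**2. Whom the rule removes at the 3-year extraction.** The Summary ends inclusion in Q2 2023, and Section 9.3.2 allows surgery up to 90 days after the inclusion visit, so the last surgery falls by about the end of September 2023 and reaches 3 years by the end of September 2026. Section 9.1 gives a longer inclusion period of 32 months. Counted from the end of June 2021, this runs to the end of February 2024; 90 days more is the end of May 2024, and 3 years more is the end of May 2027. Both dates precede Q4 2027. Nobody is then dropped for lack of calendar time, so the rule acts only on deaths and on losses from the database. Section 6 puts coverage at 99% of the population, so such losses should be few and deaths are the main concern.

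**3. Size of the bias.** Let d be the proportion dying within 3 years and k the ratio of their mean cost (or event risk) to that of survivors, m. The full-cohort mean is m(1 − d + dk) and the survivors-only mean is m. The survivors-only analysis therefore understates by 1 − 1/(1 − d + dk). The protocol gives neither d nor k, so the values below are assumptions, taken as equal in both groups with no true treatment difference.

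| d | k = 1 | k = 2 | k = 3 |
|---|---|---|---|
| 3% | 0% | 1 − 1/1.03 = 2.9% | 1 − 1/1.06 = 5.7% |
| 5% | 0% | 1 − 1/1.05 = 4.8% | 1 − 1/1.10 = 9.1% |
| 10% | 0% | 1 − 1/1.10 = 9.1% | 1 − 1/1.20 = 16.7% |

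For an event with a true risk of 20%, the restricted cohort would show 20%/1.03 = 19.4% (d = 3%, k = 2) down to 20%/1.20 = 16.7% (d = 10%, k = 3). If the SNDS comparators keep their deaths, these gaps appear as PUL versus SNDS differences. A k below 1, for instance because men who die accrue costs over less time, would reverse the sign.

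**4. Loss of numbers.** With d = 3-10%, 2.4 to 8 of 80 PUL patients are lost. The half-width at p = 50% goes from 10.96% to 11.12-11.55%, which is minor. Each lost PUL patient leaves 5 × 3 = 15 comparators without their index patient, or 36 to 120 of 1200.

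**5. Consistency with Section 11.2.1.** An intention-to-treat comparison keeps patients whatever happens after treatment, and this rule does not. Kaplan-Meier estimation is built to use incomplete follow-up, and the rule discards that information before the method is applied.

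**The case against.** The best defence is that the sentence is loosely worded and meant only that a 3-year window must be available in the database. It follows the linkage sentence, the Summary gives both the clinical and SNDS cohorts the same frame of 2 years' history and 3 years' follow-up, and the intention-to-treat and Kaplan-Meier plans suggest that the authors did not intend to remove deaths. Kaplan-Meier also remains valid when follow-up is complete. This may well be the intention, but the text says otherwise: it makes 3-year follow-up a condition of being analysed, and nothing says that a death counts as completed follow-up.

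Several stronger readings are tempting and are not supported:

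- **That the primary result is affected.** The 4-month analysis uses micro-costing, patient-declared consumption and Clavien-Dindo complications, and is scheduled for Q1-Q2 2024, before 3-year follow-up can be known. Given its place after the linkage sentence, the rule most plausibly does not reach it.
- **That the comparators are unselected and their deaths certainly kept.** They are screened on the Charlson index and matched on age, month of procedure and the disease risk score. Retention of those who die is inferred from the absence of any exclusion.
- **That the first extraction would lose patients operated on less than 3 years before it.** That extraction is labelled as 1-year follow-up. The loss arises only if the 3-year rule is imposed on it.
- **That the bias must favour PUL by a known amount.** Direction and size depend on quantities that the protocol does not give.

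The steering committee's review of major violations in Section 9.10.4 is a separate matter and adds nothing here.

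**Conclusion.** The point holds in limited form. As written, the protocol selects the PUL and TURP/laser patients of the SNDS-linked analysis on survival and continued presence in the database for 3 years. It states no equivalent condition for the SNDS cohort, and the rule conflicts with its own analysis principles. If comparators who die are retained and men who die cost more or have more events, 3-year PUL costs and events are understated relative to the SNDS controls. At assumed deaths of 3-10% and a ratio of 2-3, the understatement is about 3-17%; at a ratio of 1 it is nil. These are illustrations, not estimates.

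The sentence should be corrected before the SNDS-linked analyses. It is not a threat to the primary endpoint on the most plausible reading. Its effect on the 12-month cost/QALY analysis depends on whether the rule is applied literally.

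**What to change.** In the Summary and in Section 5.1.2, remove only the 3-year follow-up condition and keep the 2-year look-back. Deleting the whole sentence would lose the look-back as well.

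State one rule for all three cohorts: each linked or matched patient is followed from surgery to death, loss of coverage or 3 years, whichever comes first. Costs accumulate to death. Retreatment and hospitalisation are analysed with censoring at loss of coverage or 3 years, and with death as a competing event. The 1-year analyses use all linked patients whose surgery was at least 1 year before the extraction, including those who die within that year.

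The cost is small. Section 14.3 already lists date of death and costs among the data to be extracted. Section 15 keeps death to month and year, which is fine enough for a 36-month follow-up. What is added is a wording change in two places, one common follow-up rule, and slightly more analysis work for the competing event.
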